APPENDIX VII: LINEAR ANALOGUE SELF-ASSESSMENT

Directions: Please circle the number (0-10) best reflecting your response to the following that describes your feelings **during the past week, including today**

How would you describe:

1. your overall Quality of Life?

0	1	2	3	4	5	6	7	8	9	10
As bad as it can be										As good as it can be

2. your overall mental (intellectual) well being?

0	1	2	3	4	5	6	7	8	9	10
As bad as it can be										As good as it can be

3. your overall physical well being?

0	1	2	3	4	5	6	7	8	9	10
As bad as it can be										As good as it can be

4. your overall emotional well being?

0	1	2	3	4	5	6	7	8	9	10
As bad as it can be										As good as it can be

5. your level of social activity?

0	1	2	3	4	5	6	7	8	9	10
As bad as it can be										As good as it can be

6. your overall spiritual well being?

0	1	2	3	4	5	6	7	8	9	10
As bad as it can be										As good as it can be

7. the frequency of your pain?

0	1	2	3	4	5	6	7	8	9	10
No pain										Constant pain

8. the severity of your pain, on the average?

0	1	2	3	4	5	6	7	8	9	10
No pain										Pain as bad as you can imagine

9. your level of fatigue, on the average?

0 1 2 3 4 5 6 7 8 9 10
No fatigue Constant tiredness

10. your level of support from friends and family?

0 1 2 3 4 5 6 7 8 9 10
No support Highest level of support

11. your financial concerns?

0 1 2 3 4 5 6 7 8 9 10
Constant concerns No concerns

12. your legal concerns (will, advanced directives, etc.)?

0 1 2 3 4 5 6 7 8 9 10
Constant concerns No concerns

APPENDIX VIII: WAS IT WORTH IT (WIWI) QUESTIONNAIRE

Participating in a clinical trial / research study is a personal choice and an individual experience. We would like to get your feedback on your experience in this research study. Please respond to the following questions as indicated.

Directions: Please answer each question by circling Y (for yes), N (for no), or U (for uncertain).

Was it worthwhile for you to participate in this research study? Y N U

If you had to do it over, would you participate in this research study again? Y N U

Would you recommend participating in this research study to others? Y N U

Directions: In the next two questions, please answer each question by circling one response.

Overall, did your quality of life change by participating in this research study?

It improved It stayed the same It got worse

Overall, how was your experience of participating in this research study?

Better than I expected The same as I expected Worse than I expected

If there was **one thing** that could have been done to improve your experience in this research study, what would it be?

Would you like to talk to someone about your concerns (*circle one response*)? Yes No

APPENDIX IX: TOBACCO USE ASSESSMENT

Visit Number _____

Type of Visit: Phone Visit Clinic Visit**Missed visit:** Please comment below if patient canceled and reason, if rescheduled, or if a no-show.**VITAL SIGNS**

1. Height _____ cm (*without shoes*)
2. Weight _____ kg (*without shoes, with lightweight indoor clothes (no coats or jackets)*)
3. Pulse _____ bpm
4. Blood Pressure: _____ / _____ mm/Hg

TOBACCO-USE STATUS**REFERENCES:**

- a. Target Quit Day (____/____/____)
mm dd yyyy
- b. 14 Days After TQD (____/____/____)
mm dd yyyy
5. a. Since 14 days after your TQD, have you used any tobacco on each of 7 consecutive days?
9 Not applicable 0 No 1 Yes

1  cigarettes ↓	1  cigars	1  pipes	1  smokeless	1  other _____ ↓
Date of First Use: ____/____/____ mm dd yyyy				

- b. Since 14 days after your Target Quit Day, have you used any tobacco on at least one day in each of 2 consecutive weeks?
9 Not applicable 0 No 1 Yes

1  cigarettes ↓	1  cigars	1  pipes	1  smokeless	1  other _____ ↓
Date of First Use: ____/____/____ mm dd yyyy				

- c. Have you used any tobacco since your last visit? 0 No 1 Yes

1  cigarettes ↓	1  cigars	1  pipes	1  smokeless	1  other _____ ↓
Date of First Use: ____/____/____ mm dd yyyy				

d. Have you used any tobacco in the last 7 days?

0 No

1 Yes

1  cigarettes/day? _____ if less than 1/day specify → _____
1  pipe bowls/day? _____ if less than 1/day specify → _____
1  cigars/day? _____ if less than 1/day specify → _____
1  smokeless tobacco cans or pouches/week? _____ if less than 1/wk specify → _____
1  other/week → specify type and amount _____ if less than 1/wk specify → _____

BEHAVIORAL INTERVENTION

6. Since your last visit, have you had the opportunity to speak with anyone in the NCI Tobacco Quitline?

0 No →

Explain why not _____
Just a reminder that you can call the tobacco quitline at any time so that they can provide you with support during this time of trying to stop smoking. Would you like me to provide you with their toll-free number? 0  No 1  Yes → the number is [name]
Is there anything I can help you with? 0  No 1  Yes → explain _____

1 Yes →

How many times have you connected with them since our last visit? ____ _
What overall topic did you discuss? _____
Just a reminder that you can call the tobacco quitline at any time so that they can provide you with support during this time of trying to stop smoking. Would you like me to provide you with their toll-free number? 0  No 1  Yes → the number is [name]
Is there anything I can help you with? 0  No 1  Yes → explain _____

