5.0 STUDY CALENDAR

Pre-Study Testing Intervals

- To be completed \leq 16 DAYS before registration: History and physical.
- To be completed \leq 6 months before registration: Serum creatinine.

Visit week	Prior to Surgery		Day of Surgery**	Post-Surgery***			
	Prior to Registration†	Baseline*	0	6	12	18	24
Visit #	1	2		3 (A)	4 (A, B)	5 (A, B)	6
Tests and observations							
History & physical (weight, bp, pulse)	E	E		X			X
Height	X						
Serum creatinine	X						
Pregnancy test	C						
Concomitant therapies		X		X	X	X	X
Adverse events		X		X	X	X	X
Surgical adverse events				X(1)	X(1)	X(1)	X(1)
Suicidal ideation monitoring				X (2)	X (2)	X (2)	X (2)
Tobacco use assessment (Appdx IX)	X	X	X	X	X	X	X
Surgical team message		X					
NCI Smoking Quitline		X (3)		X (3)	X (3)		
Sample submission							
Salivary Cotinine Measure		X	X	X	D	D	X
Patient questionnaires							
Contemplation Ladder (Apdx III)	X			X	X		X
SEQ-12 (Apdx IV)		X		X	X		X
FTND (Apdx V)		X					
PHQ-9 (Apdx VI)	X (4)			X	X		X
LASA-12 (Apdx VII)		X			X		X
Was It Worth It Survey (Apdx VIII)					X		X
Drug and Behavioral Support Adherence Logs (Apdx X)		X		X	X		
Correlative study (optional)							
Whole blood	To be collected at baseline, see Sections 6.2 and 14.0.						

† Pre-study testing may be performed on the same day as the baseline visit (see also, Section 7.1).

* Baseline: After randomization and at the time the surgical message is discussed with the cancer patient. If performed within 7 days prior to baseline, the Tobacco Use Assessment need not be repeated.

** Surgery must occur after the TQD defined at baseline and can be performed no sooner than 10 days after randomization and no more than twelve weeks after randomization.

*** Post surgery visits can be +/- 14 days

A Patient-completed booklets for Weeks 12 and 18 should be given to patients at the Week 6 visit. Institutional staff should telephone patients within one week prior to Weeks 12 and 18 to remind them that they will either be completing these booklets by telephone at Weeks 12 and 18 or that they may bring the completed booklet to the clinic when they provide saliva samples for cotinine measurements (see Footnote D).

B May be done by telephone or in person (see footnote D).

C For women of childbearing potential. Must be done within 7 days prior to registration/randomization.

D Patients will be asked to come to the treating institution to provide saliva samples for cotinine measurement. A physician visit is not required.

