Rates of smoking abstinence will be compared between arms using Fisher's exact test and logistic regression models. Abstinence definitions are based upon the Society for Research on Nicotine and Tobacco (SRNT) Working Group recommendations.[88] The major advantage of point prevalence estimates is that they are widely reported in the literature and can be verified biochemically. However, point prevalence abstinence does not account for slips/lapses that might occur between follow-up periods. Prolonged abstinence is defined as smoking abstinence sustained after an initial 2-week grace period[88] and accounts for initial lapses. However, prolonged abstinence cannot be verified biochemically short of daily biochemical confirmations and, ultimately, must rely on self-report. Research suggests that self-reports among smokers in general tend to be accurate, and misreporting rates are generally very low.[89] We allow for a 2-week grace period after TQD based upon the SRNT Working Group recommendations.[88] Prolonged smoking abstinence will be adjudicated if the following criteria are met: 1) Self-reported smoking abstinence since 2 weeks after the TQD. This will be identified by a negative response to the question, "Since xx/xx/xxxx, which was 2 weeks after your TQD, have you smoked any tobacco, even a puff, for 7 consecutive days or at least once each week on 2 consecutive weeks?" and 2) No failed biochemical confirmation of self-reported smoking abstinence at any previous outcome assessment. Point prevalence smoking abstinence will be adjudicated if both of these criteria are met: 1) Self-reported smoking abstinence for the last 7 days. This will be identified by a negative response to the question, "Have you smoked any tobacco, even a puff, in the past 7 days?", and 2) Salivary cotinine less than 15 ng/mL. Relapse will be defined as smoking on 7 consecutive days or smoking at least once each week on 2 consecutive weeks.[88]

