14.1.2 Hypothesis/objective

This biomarker will be used to increase the accuracy of tobacco assessment as compared with self-reported tobacco use. The hypothesis is that biochemically confirmed tobacco use will increase the magnitude of difference in study outcomes as compared with self-reported tobacco use. This biomarker will be used for the following objectives:

Primary objective: To evaluate the effect of biochemically confirmed tobacco use on study outcomes

Secondary objectives:

To evaluate the accuracy of self-reported tobacco use among study participants

To evaluate if biochemically confirmed tobacco use correlates with a larger magnitude of difference in study outcomes as compared with self-reported tobacco use

To evaluate longitudinal accuracy of self-reporting among study participants at baseline and throughout the study

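### At weeks 12 and 18 the 7-day tobacco report and the saliva sample need not fall on the same day, yet they are combined and compared as if they did, so a change in smoking between the two dates can be misclassified

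*Combined protocol and SAP*

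**What the plan says.** **Timing (Section 5.0).** Weeks 12 and 18 are the two visits marked as possible by telephone (footnote B). Footnote A has staff remind patients that "they will either be completing these booklets by telephone at Weeks 12 and 18", or that they may bring the completed booklet when they give saliva. Sections 4.3 and 6.1 list Appendices II to IX as the booklet contents, so the Tobacco Use Assessment (Appendix IX) is included. For the sample, footnote D says "Patients will be asked to come to the treating institution to provide saliva samples for cotinine measurement". A further footnote says "Post surgery visits can be +/- 14 days".

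**Recall period (Appendix IX, item 5d).** The question is "Have you used any tobacco in the last 7 days", counted back from the day it is answered.

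**Scoring (Section 13.4).** Point-prevalence abstinence needs both a negative 7-day report and "Salivary cotinine less than 15 ng/mL". Prolonged abstinence tolerates isolated lapses, because relapse means 7 consecutive days of smoking or smoking in each of 2 consecutive weeks. It also requires that no earlier report of abstinence failed biochemical confirmation.

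**Accuracy (Sections 14.1.2 and 14.1.3).** One objective is "To evaluate the accuracy of self-reported tobacco use among study participants"; another follows that accuracy over time.

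**A limit that exists elsewhere.** At baseline, a previous Tobacco Use Assessment may stand only if it was done within 7 days before that visit. Weeks 12 and 18 have no counterpart.

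**The concern.** A biochemical check confirms a report only if both describe the same period. Here the report may describe one week and the sample another, and no rule says how to score a pair with different dates. Smoking status in this population is expected to change, so elapsed time alone can create disagreement.

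Three analyses depend on the pair:

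- the secondary abstinence endpoint, including prolonged abstinence at week 24, which inherits failures from weeks 12 and 18;
- the self-report accuracy objectives, where elapsed time would be mixed with real misreporting at the two telephone-optional visits only, and could look like a change in accuracy over follow-up;
- the genetic substudy, whose abstinence outcome uses the tobacco assessment with cotinine and names week 12 as a time point (Section 13.5.2).

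**Working it through.** The plan states no figure for the gap or its effect, so there is none to reproduce.

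**Step 1: the possible gap.** Input: a window of 14 days either side of the nominal week (Section 5.0). If the window applies separately to the report and to the sample, the largest gap is 14 + 14 = 28 days. The recall period is 7 days, and 28 / 7 = 4 recall periods.

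**Step 2: what happens to a pair that straddles a change.** I read a failed confirmation as reported abstinence with a sample that is not below the cutoff, and I assume the sample reflects smoking status when it is taken.

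| Sequence | Scored from different days | Scored from a same-day answer |
|---|---|---|
| Truthful no by telephone, one lapse, positive sample | Not abstinent; failed confirmation; report looks inaccurate | Answer is yes: not abstinent; no failed confirmation; report and sample agree |
| Positive sample while smoking, then stops, truthful no more than 7 days later | As above | As above |
| Truthful yes by telephone, then stops, negative sample more than 7 days later | Not abstinent; report and sample disagree | Answer is no: abstinent; report and sample agree |

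In the first two rows the point-prevalence result on the sample date is the same either way. What changes is the failed confirmation, which carries forward, and the accuracy count. In the third row point prevalence itself changes. The first row also works against the lapse tolerance in Section 13.4: one isolated lapse, truthfully reported on the sample date, would not bar prolonged abstinence, but the same lapse falling in the gap would.

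**Step 3: size, by assumption.** The documents give no rate of return to smoking. Let *r* be the share of abstainers who resume per week and *g* the gap in weeks, with the report first. If every resumption is still detectable at the saliva trip, the share of truthful reports of abstinence that are contradicted is 1 − (1 − *r*)^*g*.

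| *r* (assumed) | *g* = 2 | *g* = 4 |
|---|---|---|
| 2% per week | 1 − 0.98² = 4.0% | 1 − 0.98⁴ = 7.8% |
| 5% per week | 1 − 0.95² = 9.8% | 1 − 0.95⁴ = 18.5% |

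These are upper bounds for the assumed rates, because a brief lapse early in the gap may no longer show in the sample.

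**Step 4: a second set of assumptions.** Suppose instead that a share *q* change status per 28 days, with *q* from 5% to 20%. Then 1 − (1 − *q*)^(days/28) gives 1.3% to 5.4% at 7 days, 2.5% to 10.6% at 14 days and 5% to 20% at 28 days. The order of magnitude is the same. At a gap of zero, both formulas give zero.

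**The case against.** **The window belongs to the visit.** The form and the sample sit in the same calendar column, footnote A ties both to the nominal week, and bringing the booklet to the saliva trip is a named route. This stands in part. A reader might infer that the plan allows a 28-day gap; it does not say so. Twenty-eight days is a worst case derived from the window, and many sites may pair the two. But nothing requires pairing, and a booklet brought to the clinic may have been filled in earlier.

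**Other data would reveal a mismatch.** Samples carry date and time (Section 6.2.2), Appendix IX records telephone or clinic visit, and item 5c asks for the date of first use since the last visit. Section 14.1.3 also plans parallel analyses by self-report. This stands as far as it goes: self-report analyses are unharmed and some mismatches could be traced. No scoring rule uses these data. The schedule of forms is not in the documents, so a repeat of item 5d on the case report form cannot be ruled out.

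**The stakes are small.** Section 2.0 says cessation is not the focus, and Section 2.2.6 treats abstinence as a covariate of the primary outcome. That covariate is smoking status at surgery (Section 13.3), when both measures are scheduled on the same day. This stands, and limits the point to secondary and correlative analyses.

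**A misleading yardstick.** A reader might set these percentages against the 30-40% misreporting cited in Sections 13.5.1 and 14.1.1. That figure has current smokers as its denominator; mine has truthful abstainers. Nor does Section 14.1.2 set it as a target. The two should not be compared.

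**Conclusion.** The point holds as a measurement weakness at weeks 12 and 18. As written, the plan allows a report and a sample from different dates to be scored as a pair, so a patient whose status changes in between can be misclassified for point prevalence, carry a failed confirmation into prolonged abstinence, or be counted against self-report accuracy. The harm is conditional on such a change, and its size is unknown. The bounds of 4.0% to 9.8% at 2 weeks and 7.8% to 18.5% at 4 weeks rest on assumed weekly rates, on full detectability, and, for 4 weeks, on the inferred maximum gap.

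Two stronger readings are not supported. A reader might infer that the plan brands honest patients as misreporters; the documents speak only of failed confirmation and of evaluating accuracy. A reader might also infer a biased treatment comparison; both blinded arms follow the same schedule, and no direction of bias between them is shown. The Fisher test on complications and smoking status at surgery are untouched. Week 24 is not a telephone visit and is affected only through prolonged abstinence.

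**What to change.** At weeks 12 and 18, ask item 5d again when saliva is collected, and record the date of the answer. Then:

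- use that same-day answer with the sample for point-prevalence abstinence, for failed confirmation and for the Section 14.1.2 accuracy analyses;
- keep telephone-only answers for the self-report analyses;
- leave pairs from different days out of the accuracy tables.

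This takes one line each in the Study Calendar, Section 13.4 and Section 14.1.3. The cost is one repeated question at a trip already planned, and the loss of some pairs where the question was not repeated. No visit or sample is added. The change does not deal with a patient who stops smoking shortly before an announced saliva trip; that weakness exists at every scheduled visit and is separate.

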APPENDIX X: DRUG AND BEHAVIORAL ADHERENCE LOG

Date of Baseline Visit: _____

This log applies to: (circle one)	Weeks 1-6	Weeks 7-12
--	-----------	------------

	Day		Varenicline/ placebo dose taken Circle One	Did you contact the tobacco Quitline on this day? Circle One	Number of Cigarettes Smoked	Comment
Date: _____	1	AM	Yes No	Yes No		
Date: _____	2	AM	Yes No	Yes No		
Date: _____	3	AM	Yes No	Yes No		
Date: _____	4	AM	Yes No	Yes No		
		PM	Yes No			
Date: _____	5	AM	Yes No	Yes No		
		PM	Yes No			
Date: _____	6	AM	Yes No	Yes No		
		PM	Yes No			
Date: _____	7	AM	Yes No	Yes No		
		PM	Yes No			
Date: _____	8	AM	Yes No	Yes No		
		PM	Yes No			
Date: _____	9	AM	Yes No	Yes No		
		PM	Yes No			
Date: _____	10	AM	Yes No	Yes No		
		PM	Yes No			

	Day		Varenicline/ placebo dose taken Circle One	Did you contact the tobacco Quitline on this day? Circle One	Number of Cigarettes Smoked	Comment
Date: _____	11	AM	Yes No	Yes No		
		PM	Yes No			
Date: _____	12	AM	Yes No	Yes No		
		PM	Yes No			
Date: _____	13	AM	Yes No	Yes No		
		PM	Yes No			
Date: _____	14	AM	Yes No	Yes No		
		PM	Yes No			
Date: _____	15	AM	Yes No	Yes No		
		PM	Yes No			
Date: _____	16	AM	Yes No	Yes No		
		PM	Yes No			
Date: _____	17	AM	Yes No	Yes No		
		PM	Yes No			
Date: _____	18	AM	Yes No	Yes No		
		PM	Yes No			
Date: _____	19	AM	Yes No	Yes No		
		PM	Yes No			
Date: _____	20	AM	Yes No	Yes No		
		PM	Yes No			
Date: _____	21	AM	Yes No	Yes No		
		PM	Yes No			

	Day		Varenicline/ placebo dose taken Circle One	Did you contact the tobacco Quitline on this day? Circle One	Number of Cigarettes Smoked	Comment
Date: _____	22	AM	Yes No	Yes No		
		PM	Yes No			
Date: _____	23	AM	Yes No	Yes No		
		PM	Yes No			
Date: _____	24	AM	Yes No	Yes No		
		PM	Yes No			
Date: _____	25	AM	Yes No	Yes No		
		PM	Yes No			
Date: _____	26	AM	Yes No	Yes No		
		PM	Yes No			
Date: _____	27	AM	Yes No	Yes No		
		PM	Yes No			
Date: _____	28	AM	Yes No	Yes No		
		PM	Yes No			
Date: _____	29	AM	Yes No	Yes No		
		PM	Yes No			
Date: _____	30	AM	Yes No	Yes No		
		PM	Yes No			
Date: _____	31	AM	Yes No	Yes No		
		PM	Yes No			
Date: _____	32	AM	Yes No	Yes No		
		PM	Yes No			

	Day		Varenicline/ placebo dose taken Circle One	Did you contact the tobacco Quitline on this day? Circle One	Number of Cigarettes Smoked	Comment
Date: _____	33	AM	Yes No	Yes No		
		PM	Yes No			
Date: _____	34	AM	Yes No	Yes No		
		PM	Yes No			
Date: _____	35	AM	Yes No	Yes No		
		PM	Yes No			
Date: _____	36	AM	Yes No	Yes No		
		PM	Yes No			
Date: _____	37	AM	Yes No	Yes No		
		PM	Yes No			
Date: _____	38	AM	Yes No	Yes No		
		PM	Yes No			
Date: _____	39	AM	Yes No	Yes No		
		PM	Yes No			
Date: _____	40	AM	Yes No	Yes No		
		PM	Yes No			
Date: _____	41	AM	Yes No	Yes No		
		PM	Yes No			
Date: _____	42	AM	Yes No	Yes No		
		PM	Yes No			

APPENDIX XI: GENERAL THORACIC SURGERY DATABASE DEFINITIONS

Complication	Definition
Air leak	Patient experienced a postoperative air leak for >5 days
Bronchoscopy for atelectasis	Postoperative atelectasis documented clinically or radiographically that needed bronchoscopy
Pneumonia	
Defined according to the last CDC criteria: two or more serial chest radiographs with at least one of the following:
 
 • New or progressive and persistent infiltrate • Consolidation • Cavitation 
and at least one of the following:
 
 • Fever (>38°C or >100.4°F) with no other recognized cause • Leukopenia (<4000 WBC/mm³) or leukocytosis (≥12,000 WBC/mm³) • For adults ≥70 years old, altered mental status with no other recognized cause 
and at least two of the following:
 
 • New onset of purulent sputum, or change in character of sputum, or increased respiratory secretions, or increased functioning requirements • New onset or worsening cough, or dyspnea, or tachypnea • Rales or bronchial breath sounds 
Worsening gas exchange (e.g. O₂ desaturations [eg, PaO₂/FiO₂ ≤240], increased oxygen requirements, or increased ventilator demand)

ARDS	
Adult respiratory distress syndrome defined according to the American-European consensus conference; all of the following criteria should be met:
 
 • Acute onset • Arterial hypoxemia with PaO₂/FIO₂ ratio <200 (regardless of PEEP level) • Bilateral infiltrates at chest radiograph or CT scan • No clinical evidence of left atrial hypertension or pulmonary artery occlusive pressure <18 mm Hg • Compatible risk factors
Bronchopleural fistula	Patient experienced a complete or partial dehiscence of the bronchial stump documented in the postoperative period (such as bronchoscopy or other operative intervention)

Pulmonary embolism	Patient experienced a pulmonary embolus in the postoperative period as documented by a V/Q scan, angiogram, or spiral CT
Initial ventilator support	Patient initially was ventilated >48 hours in the postoperative period; ventilator support ends with removal of endotracheal tube or, if the patient has a tracheostomy tube, until no longer ventilator dependent
Reintubation	Patient was reintubated during the initial hospital stay after the initial extubation; this may include patients who have been extubated in the operating room and require intubation in the postoperative period
Tracheostomy	Patient required a tracheostomy in the postoperative period whether performed in the ICU or the OR; prophylactic minitracheostomy on the day of operation should not be considered a complication
Atrial arrhythmia	New onset of atrial fibrillation/flutter (AF) requiring medical treatment or cardioversion; does not include recurrence of AF that was present preoperatively
Ventricular arrhythmia	Sustained ventricular tachycardia or ventricular fibrillation that has been clinically documented and treated by ablation therapy, implantable cardioverter defibrillator, permanent pacemaker, pharmacologic treatment, or cardioversion
Myocardial infarction	Evidenced by one of the following criteria: 
 • Transmural infarction diagnosed by the appearance of a new Q wave in two or more contiguous leads on ECG • Subendocardial infarction (non Q wave) evidenced by clinical, angiographic, electrocardiographic signs • Laboratory isoenzyme evidence of myocardial necrosis
Empyema	Patient experienced an empyema requiring treatment in the postoperative period; diagnosis of empyema should be confirmed by thoracentesis; frank pus or merely cloudy fluid may be aspirated from the pleural space; the pleural fluid typically has leukocytosis, low pH (<7.20), low glucose (<60 mg/dL), high lactate dehydrogenase, and elevated protein and may contain infectious organisms
Wound infection	Patient experienced a wound infection in the postoperative period as evidenced by meeting two of the following criteria: 
 • Wound opened with excision of tissue (I&D) • Positive culture • Treatment with antibiotics

Cerebrovascular complications	
Occurrence of one of the following central neurologic postoperative events not present preoperatively:
 
 • A central neurologic deficit persisting postoperatively for more than 72 hours • A transient neurologic deficit (transient ischemic attack or reversible ischemic neurologic deficit) with recovery within 72 hours. • A new postoperative coma persisting at least 24 hours and caused by anoxic/ischemic and/or metabolic encephalopathy, thromboembolic event, or cerebral bleed
Recurrent nerve palsy	Patient experienced in the postoperative period a recurrent laryngeal nerve paresis or paralysis that was not identified during the preoperative evaluation
Delirium	Patient experienced a new onset of symptoms like illusions, confusion, cerebral excitement in the postoperative period
Renal failure	
Defined as the onset of new renal failure in the postoperative period according to one of the following criteria:
 
 • Increase of serum creatinine to >2.0 mg/dL • Two times the preoperative creatinine level • A new requirement for dialysis postoperatively
Chylothorax	
Patient experienced a chylothorax in the postoperative period that required persistent or new drainage and medical intervention (e.g. NPO, TPN) or reoperation.
 
Chylothorax is defined by the clinical appearance of the pleural fluid or the presence of pleural fluid triglyceride levels >110 mg/dL with a cholesterol level <200 mg/dL

Unexpected admission to the ICU	An unplanned transfer of the patient to the ICU owing to deterioration in the condition of the patient requiring active life support treatment

